Furthermore, the RN and RP will also seek permission from the respective consultant in-charge of patient's care prior to enrolling the patient into this research.

The following generic data will be captured regarding the following at each study site:

- Number of patients triaged or screened.
- Number of patients stratified as 'low risk' and 'high risk'.
- Proportion of 'low risk' patients that agreed to undergo DPC and/or interview study.
- Time taken for informed consent process.
- Time taken to conduct DPC including completion of study documentation and follow up.
- Proportion of DPC tested patients deemed test negative.
- Proportion test negative patients whose hospital electronic health record is updated.

DPC procedure: This procedure will be carried out in a safe clinical environment under clinical supervision with immediate access to cardiopulmonary resuscitation and access to a critical care team. A standardised proforma will be used to capture data (Appendix – 11.05).

Steps for DPC are listed as follows:

- 1. The research team will confirm that antihistamines have not been taken during the 3 days prior to the DPC
- 2. A urine pregnancy test should be performed for female participants of child bearing potential prior to commencing the DPC. If the test is positive, the participant will be excluded from the study.
- 3. Check baseline vital parameters (heart rate, blood pressure, SPO₂).
- 4. After confirming patient suitability with study consultant, administer oral amoxicillin (single dose 500mg).
- 5. Monitor patient signs and symptoms of allergy for 60 minutes following DPC.
- 6. Repeat vital parameters.
- 7. Complete study proforma.

Patients will receive a full therapeutic course of appropriate penicillin antibiotics as deemed necessary by their respective clinical team to treat any intercurrent infection after exclusion of type-1 HSR. This will involve discussion between research team and respective clinical team.

Alternatively, in those who do not require penicillin (opportunistic de-labelling) during current admission, a modest dose of 250mg twice daily for 3 days will be given. This is usually conducted for the following clinical scenarios:

- 1. temporal association is unclear from clinical history with respect to index reaction/s.
- 2. index reaction/s delayed in onset, i.e., not after the first dose but occurs during a course of treatment (eg: day 2 or day 4 of treatment).

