Patients who commence opportunistic de-labelling and then develop an intercurrent infection that requires a full therapeutic course of amoxicillin or an alternative penicillin antibiotic, could be switched to the appropriate treatment regimen following discussion between research team and respective clinical teams. The modest dose (250mg) of amoxicillin used for opportunistic de-labelling must be withdrawn/amended at this stage. This must be clearly recorded in the patient notes and in relevant study documentation

Follow up and advice (all patients):

Patients will be provided with a 'participant note' (Appendix – 11.06) and counselled prior to discharge and provided with written guidance regarding seeking urgent medical attention (call 999) or calling their GP if needed. In those who have temporarily withdrawn antihistamine for the DPC, specific advice will be given by the research team regarding recommencement of antihistamine following completion of DPC.

• All patients will be either reviewed (if they are still an inpatient) or contacted via telephone or virtual platform (if discharged) on day 5 to establish clinical tolerance and exclude a delayed reaction. Patients will be contacted by the research team on the next working day, if day 5 follow up call falls on a weekend or a national bank holiday and this will be recorded in study documentation retrospectively. Patients will be advised to contact the research team in case they develop a delayed-onset symptoms either before or after day 5.

De-labelling and communication to patient and GP:

- 1. The outcome of the DPC will be discussed with the patient, communicated in writing via post or electronically to their GP (Appendix 11.07) and hospital records updated accordingly. A 'wallet card' stating DPC outcome will be provided for patients.
- 2. For the 'high risk' group and those declining DPC, the outcome of risk stratification will be communicated in writing or electronically to their GP (Appendix 11.07), to enable appropriate follow up in accordance with national guidelines^{18,24}.

WS-1 Output* and data analysis: Pseudo anonymised data will be entered at each study site on a standardised spreadsheet or other software programmes and the following descriptive statistics will be generated:

- 1. Demographics analysis including age, gender and ethnicity.
- 2. Total number triaged.
- 3. Analysis of reasons for failed progression from triage to DPC.

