- 4. Time taken to complete screening log and risk stratification proforma.
- 5. Overall proportion stratified as 'low risk' and high risk'.
- 6. Overall proportion of 'low risk' that agreed to undergo DPC.
- 7. Overall proportion of patients declining to undergo DPC.
- 8. Proportion of those stratified as 'high risk' and 'low risk' (those declining DPC) meeting national criteria¹⁸ for referral to an allergy specialist for PenA skin tests.
- 9. Outcome of DPCs:
 - a. Proportion successfully de-labelled.
 - b. Description of adverse reactions (immunological or nonimmunological).
 - c. Proportion of patients that did not complete DPC with description (eg: those that undergo first dose of DPC and then opt out of the study).
 - d. Proportion of 'dropouts' with description (eg: those that express interest and default appointment at DPC).
 - e. Proportion of immediate (including severity as per international grading system^{37,38}) and nonimmediate HSRs (descriptive analysis) and other adverse reactions and treatment received.

*Descriptive data regarding inter-site and inter-clinical setting will be summarised as N=(%)

Patient pathways for WS1 are summarised in Appendices 11.08 and 11.09.

A total number of 122 DPCs will be conducted across the 3 participating centres in the above clinical settings. In the event that the recruitment targets are not met at an individual centre, other centres will aim to compensate with additional participants to achieve the proposed number of DPCs.

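### The fixed 3-day course ends before or just at the protocol's own day-4 example of a delayed index reaction, yet the day-5 contact is used to exclude a delayed reaction

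*Protocol*

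**What the plan says.** All of this stands in Protocol section 10.4.3.3 unless another section is named.

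- **Challenge.** On the challenge day the team is to "administer oral amoxicillin (single dose 500mg") and observe for 60 minutes.
- **Patients with an infection.** "Patients will receive a full therapeutic course of appropriate penicillin antibiotics as deemed necessary by their respective clinical team".
- **Patients who do not need penicillin (opportunistic de-labelling).** "a modest dose of 250mg twice daily for 3 days will be given". The text continues: "This is usually conducted for the following clinical scenarios". The first scenario is unclear timing of the index reaction. The second is a reaction that came after the first dose and "occurs during a course of treatment (eg: day 2 or day 4 of treatment").
- **Follow-up.** All patients are reviewed or called "on day 5 to establish clinical tolerance and exclude a delayed reaction". The contact moves to the next working day if day 5 is a weekend or bank holiday. In addition: "Patients will be advised to contact the research team in case they develop a delayed-onset symptoms either before or after day 5".
- **Records.** The Schedule of Procedures (section 10.10) places the final outcome, the hospital-record update and the letter to the general practitioner at the day-5 follow-up.
- **Outcome.** Under WS-1 Output and data analysis, item 9a is "Proportion successfully de-labelled". Item 9e covers immediate and non-immediate hypersensitivity reactions.

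**The concern.** The protocol describes the delayed index reaction by the day of treatment on which it occurred. The course length is fixed and is not tied to that day. If dosing stops before the treatment day on which the first reaction appeared, a symptom-free day-5 contact shows tolerance of the exposure given. It does not show what would have happened on a treatment day that was never reached.

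The protocol makes no such distinction. One day-5 rule serves every patient, and items 9a and 9e do not separate patients by how far exposure went. The de-labelling proportion is the quantity on which the 122 challenges are sized (section 10.4.7), and challenge outcomes feed the economic model (section 10.4.5). At stake is what the study can claim about delayed tolerance, and what is written in the records of these patients.

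**Working it through.** **The plan's own figure.** Section 10.4.7 gives an expected rate of about 97%, a 95% interval of ±3 points and 122 challenges. The usual formula is n = z² p(1 − p)/d². With z = 1.96, p = 0.97 and d = 0.03:

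n = 3.8416 × 0.0291 / 0.0009 = 124.2, rounded up to 125.

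The stated 122 agrees within rounding of the rate: p = 0.9705 gives 122.2, and the half-width at n = 122 with p = 0.97 is 3.03 points. Course length does not enter the formula, so the sample size does not depend on this point.

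**Inputs for the day count** (section 10.4.3.3): one 500 mg dose on the challenge day; then 2 doses a day for 3 days, which is 6 doses; index-reaction examples on day 2 and day 4 of treatment; contact on day 5. The protocol does not say whether the course starts on the challenge day or the next day, or whether the challenge day is day 0 or day 1. I count the challenge as day 1, the first day of exposure. Last dosing day = start day + 2.

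| Course starts | Dosing days | Last dosing day | Day-2 example | Day-4 example | Last dose to day-5 contact |
|---|---|---|---|---|---|
| Same day | 1 to 3 | 1 + 2 = 3 | passed | no dose on that day | 5 − 3 = 2 days |
| Next day | 1 to 4 | 2 + 2 = 4 | passed | final dosing day | 5 − 4 = 1 day |

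If a same-day start leaves room for only one 250 mg dose on day 1, the sixth dose falls early on day 4. That still only just reaches the example. If day 5 means five days after the challenge (day 6 on this count), the gaps become 3 and 2 days.

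**Later index reactions.** Day 4 is introduced as an example, not as a maximum. The low-risk list limits how long ago a reaction happened in one criterion (more than 10 years), but nowhere limits how many days into treatment it began. A patient whose index reaction began after day 4 can qualify as low risk, and neither reading of the start day gives a dose on that day.

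**Side by side.** The course covers one of the two examples fully and the other not at all or only on its last day. The follow-up rule and the schedule treat both alike: delayed reaction excluded, outcome final, record updated.

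**Scale.** One patient in 122 is 1/122 = 0.82 percentage points of the de-labelling proportion. This is a unit of measure, not an estimate: the document gives neither the number of patients with late index reactions nor their reaction rate.

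**The case against.** The strongest reply is that the protocol nowhere requires exposure to last as long as the index latency. The timing of the index reaction and the length of the course are stated separately. Whether 500 mg plus three days would reveal a delayed reaction is a clinical question that the document cannot settle. This stands. A reader might infer that the protocol contradicts itself, or that a delayed reaction may count as excluded only once exposure has reached the index day. The text supports neither; the second would be a new clinical rule.

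Other parts of the reply also stand:

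- The course is usual rather than mandatory in these scenarios. It applies only to patients who do not need penicillin; the others get a therapeutic course, and a switch is allowed.
- The day-2 example is covered on both readings.
- Observation runs to day 5, and patients are told to report symptoms after it. A late reaction to the doses given could still be seen.
- Item 9a has no stated definition. That such patients count as de-labelled is likely from the schedule, but it is an inference, and a definition may stand in an analysis plan that is not shown.
- In many patients the index day cannot be known: unclear timing, childhood rash without details, gaps in the history, or a label based on family history alone.

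What the reply does not remove is the difference between observing and exposing. The index event is described as arising during treatment, and contact after dosing has stopped cannot supply a treatment day that was not given.

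**Conclusion.** The point holds in a limited form. For patients on the 3-day course whose index reaction came on day 4 or later, dosing stops before or just at the index day. To say that the day-5 contact *excludes* a delayed reaction then claims more than the design shows. This rests on counting the challenge as day 1 and holds for either start day.

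A reader might go further and infer that the de-labelling proportion is biased upward, non-immediate reactions are undercounted, or patients are wrongly de-labelled. Those are possible directions, not demonstrated effects: the document gives no number of affected patients and no reaction rate among them. The sample size of 122 stands, and no stop/go metric in section 10.4.6 uses the de-labelling proportion. The consequence is for the wording and reporting of delayed tolerance.

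**What to change.** 1. **Reconcile the DPC procedure and follow-up text of section 10.4.3.3 with the schedule in section 10.10.** State the start day of the course, the day numbering, how the course length relates to the day-4 example, and what the day-5 contact can establish. The clinical leads decide how; no dose, duration or clinical criterion is proposed here.
2. **Record two items:** the index-reaction day where known, and the last-dose day. The proformas are not shown and may already hold them.
3. **Present items 9a and 9e descriptively in three groups:** exposure reached the index day; exposure did not reach it; index day unknown or no index episode. For the second group, state that tolerance beyond the exposure period was not tested.

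The cost is protocol wording, up to two data fields and a slightly more qualified de-labelling figure. No patients or visits are added.

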10.3.2 Secondary

- To assess the proportion of 'low risk' patients with a PenA label who would be eligible for a DPC.
- To assess the proportion of 'low risk' patients who would be willing and complete a DPC.
- To explore practical aspects of implementing this de-labelling programme in secondary care by investigating factors such as organisational context, treatment pathway, protocol implementation, time taken and resources.
- To evaluate the potential cost-effectiveness of this service model.

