10.4.3 WS1

10.4.3.1 WS-1 objective:

- To provide a demographic description of PenA labels in AMU/ID units, Haematology-Oncology units and pre-surgical units.
- 2. To provide reasons for failure to progress from triage to DPC.
- 3. To determine the mean time taken to complete screening log and risk stratification proforma.
- 4. To determine the proportion of study eligible patients stratified as 'low risk' and 'high risk'.
- 5. To provide a descriptive analysis of DPC uptake and outcomes.
- 6. To determine the proportion of patients meeting national criteria for referral to an allergy specialist for PenA skin tests.

10.4.3.2 Inclusion and exclusion criteria for initial triage process:

Inclusion criteria:

Patients with a current PenA label, ≥18 years, willing and able to give informed consent Exclusion criteria:

- Clinically unstable patients, i.e., unstable cardio-respiratory status (eg: respiratory failure, cardiac failure, pre-hepatic encephalopathy etc.)
- History of serious non-immediate systemic hypersensitivity reactions (HSRs) to penicillin
 - Documented Steven Johnson syndrome (SJS), toxic epidermal necrolysis (TENS), acute exanthematous generalised pustulosis (AEGS), erythema multiforme, haemolytic anaemia, vasculitis, acute interstitial nephritis
- Those deemed unsuitable for medical reasons (unlikely to comply with study protocol)
- Pregnant
- Breast feeding
- Concomitant COVID-19 infection (patients from pre-surgical units and Haematology-Oncology units may be considered following recovery from COVID-19)

- Those participating in any other research currently or those who have participated in research involving medicinal product, medical devices and/or other intervention in preceding 6weeks.
- Patients currently receiving Omalizumab or those who have received Omalizumab within 6 months prior to proposed DPC
- Patients currently taking antihistamine and are unable to temporarily withdraw this medication for the proposed DPC

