A list of patients meeting initial triage criteria will then be forwarded by the RN/RP performing the initial eligibility screening to the RN or RP conducting the risk stratification process for a DPC. Having sought permission from the clinical care team, the RN/RP will approach patients and give them a patient information sheet (Appendix 11.02). A minimum period of 4-6 hrs will be given for them to consider participation and prior to informed consent. Patients will also be given an option to take additional time for consideration to participate. In those patients where the clinical care team identify a need of urgency for the administration of a penicillin antibiotic and/or in those who are keen and have understood the information provided regarding this research study, informed consent will be sought within an hour after the patient information sheet is issued. This will align well with the rapid turnaround times within acute medical unit and offer opportunities for opportunistic and therapeutic delabelling. The RN/RP will then return to the wards and ask the patient if they wish to participate in the study. An informed consent (Appendix-11.02) will be obtained by RN/RP at this stage prior to systematic stratification as 'low risk' and 'high risk' (described in later section). This will be conducted by RPs who have undergone studyspecific training in Oxford and Birmingham sites and RNs who have undergone study-specific training in Leeds. Evidence of training will be documented in the respective site files. A nominated Consultant Physician will provide clinical support to the RP/RN. The risk stratification process will be standardised on a proforma (Appendix-11.03) across all sites and appropriate training delivered to the study team at a pre-study workshop. A paper copy or an electronic copy of the duly signed consent form will be

forwarded by the research team to patient's general practitioner by post or electronically respectively and the patient will be made aware of this prior. A copy of the consent form will be filed in patient's hospital notes or electronic records at respective site files. Consent will also be documented in hospital notes.

We will display posters (Appendix – 11.04) in these units to advertise the study.

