The study RN or RP will obtain an informed consent (this may be a verbal consent at this stage but will be recorded in the study documentation) prior to risk stratification. This will be conducted either in an interview face-to-face or on a virtual platform or *via* telephone. Those consenting over telephone or virtually will be advised to email or post the signed consent form to the study team in a prepaid self-addressed envelope or bring it with them to the DPC appointment. A paper copy or an electronic copy of the duly signed consent form will be forwarded by the research team to patient's general practitioner by post or electronically respectively and the patient will be made aware of this prior. A copy of the consent form will be filed in patient's hospital notes or electronic records and at respective site files. Consent will also be documented in hospital notes.

Patients will be risk stratified by RN or RP as described in previous section, and those deemed 'low risk' will be invited for a DPC on an elective basis. There will be a nominated Consultant Physician and Consultant Anaesthetist providing clinical support and clinical cover to RN/RP for Haematology Oncology units and pre-surgical units respectively.

Inclusion and Exclusion Criteria for DPC:

Risk stratification process: This will be conducted using a standardised proforma and criteria (summarised in the next section; Appendix 11.03). This will also involve review of previous prescription and health records or/and a phone call to patient general practice (GP) surgery for additional clarification as deemed necessary. Patients will be stratified as 'low risk' and 'high risk'. The risk stratification criteria are adapted from a system described by us and others previously^{1,6,14}. This is as follows:

Low Risk: Those with one or more of the following:

- history of nonspecific symptoms *only* (eg: headache, isolated dizziness, gastrointestinal symptoms).
- Thrush only, no other symptoms.
- mild 'benign#' rash.
- History of 'childhood rash no further details available'
- Pruritus without rash.
- those with gaps in clinical history, but history is clearly suggestive of a non-life threatening reaction and did not require hospitalisation.
- Remote (>10 years) reactions without features of an IgE mediated reaction.
- Tolerated treatment with amoxicillin/co-amoxiclav since registration of PenA label.

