Construction of decision-analytic model: A study team meeting (month 18) will be convened to represent the decision-analytic model structure and explore whether the results from WS 1 and 2 have led to any changes to the proposed PenA de-labelling programme or highlighted any additional scenarios that we need to explore in the economic modelling. The model will then be constructed (months 18-24) in line with the International Society for Pharmacoeconomics and Outcomes Research (ISPOR) good practice recommendations⁴⁵. The model will compare the cost-effectiveness of the proposed PenA de-labelling programme with current practice. The model will conceptualise patients passing through the pathway and allow estimation of the potential impact of introducing the PenA delabelling programme on patient health and costs. Data from the study will be used to inform model parameters, including but not limited to patient characteristics, proportion stratified into 'low risk' and 'high risk' groups and DPC outcomes. A NHS and personal and social services perspective will be adopted, in line with NICE recommendations. Key model outcomes will include incremental costeffectiveness ratios (ICERs) and net health benefit. Probabilistic analysis will be used to account for and describe uncertainty in model parameter estimates. Scenario analyses will be conducted to help understand the impact of any assumptions made or regional differences in patient management previously identified.

Value of information analysis: Based on our decision-analytic model, we will use value of information analysis⁴⁶ to estimate the expected value of perfect information (EVPI) which can be used to guide whether it is of value to collect further data to reduce the probability of making the 'wrong' decision. We will also calculate the expected value of perfect parameter information (EVPPI) which estimates the value of removing uncertainty in specific model parameters. These analyses will be used to help determine whether further research is needed and also guide future study designs.

Engagement with service managers: The results of the economic modelling will be presented to service managers at each of the 3 study sites to explore their perspective on the economic viability of the proposed PenA de-labelling programme and to ascertain what, if any, further evidence they would require to adopt the programme at their hospital.

10.4.6 'Stop/Go' criteria

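### Willingness to undergo DPC is measured only among patients who have already consented to the DPC study, so it overstates willingness among labelled low-risk patients if non-consenters are less willing

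*Protocol*

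**What the plan says.** The secondary objective (Protocol 10.3.2) is "To assess the proportion of 'low risk' patients who would be willing and complete a DPC". Secondary outcome b in 10.3.3 and item 6 of the WS-1 output in 10.4.3.3 turn this into a percentage of low-risk patients: "Overall proportion of 'low risk' that agreed to undergo DPC".

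The recruitment steps in 10.4.3.3 fix who can be in that denominator. For the acute medical and infectious diseases units: "A list of patients meeting initial triage criteria will then be forwarded by the RN/RP performing the initial eligibility screening". The patient then receives the information sheet, and consent "will be obtained by RN/RP at this stage prior to systematic stratification as 'low risk' and 'high risk". For the pre-surgical and Haematology-Oncology units, consent may be verbal at this stage but "will be recorded in the study documentation) prior to risk stratification". The triage inclusion criterion in 10.4.3.2 is "Patients with a current PenA label, ≥18 years, willing and able to give informed consent".

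WS1 objective 4 (10.4.3.1) is "To determine the proportion of study eligible patients stratified as 'low risk' and 'high risk". For the economic model, 10.4.5 names among its study-derived inputs "proportion stratified into 'low risk' and 'high risk' groups and DPC outcomes", in a list that is expressly not exhaustive.

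The protocol also plans to report the total triaged and to analyse why patients do not get from triage to DPC (WS1 objective 2; WS-1 output items 2 and 3).

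**The concern.** A patient is classified as low risk only after agreeing to join a study whose central procedure is the DPC. Someone who reads the information sheet, does not want to be given penicillin and says no leaves before stratification. That refusal expresses the very unwillingness that outcome b is meant to measure, yet it cannot enter the numerator or the denominator.

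The service model in 10.2.2 works differently: labelled patients are stratified from history and records, and the low-risk ones are then offered a DPC. A Trust planning that service needs uptake among its labelled low-risk patients. The study will report uptake among those who have already passed a consent step that the service description does not contain. If the two are read as the same quantity, the acceptability of the service is overstated.

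**Working it through.** **The plan's own figure.** The only calculated figure is the 122 DPCs in 10.4.7, for a de-labelling rate of about 97% with a 95% interval of ±3 points. The normal-approximation formula gives 1.96² × 0.97 × 0.03 / 0.03² = 124.2, rounded up to 125. At n = 122 the half-width is 3.03 points. The stated number is reproduced closely enough. It concerns outcomes among DPCs performed, so it neither depends on nor sizes the willingness estimate.

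**Order of steps.** Triage, information sheet, consent, stratification, offer of DPC. The sequence is the same in every clinical setting, so low-risk status exists only for consenters.

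**Inputs.** None of these is given in the document; all are assumptions.
- c: share of approached low-risk patients who consent to the study
- w: share agreeing to DPC among consented low-risk patients (what item 6 reports)
- u: share of non-consenting low-risk patients who would accept a DPC

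**Formula.** Willingness among all approached low-risk patients = c·w + (1-c)·u.

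Overstatement = w - [c·w + (1-c)·u] = (1-c)(w-u). It is positive whenever u < w and zero if u = w or c = 1.

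**Numbers, with w = 90%:**

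| c | u | c·w + (1-c)·u | Overstatement |
|---|---|---|---|
| 40% | 0 | 0.36 + 0 = 36% | 0.60 × 0.90 = 54 points |
| 80% | 0 | 0.72 + 0 = 72% | 0.20 × 0.90 = 18 points |
| 40% | 50% | 0.36 + 0.30 = 66% | 0.60 × 0.40 = 24 points |
| 80% | 50% | 0.72 + 0.10 = 82% | 0.20 × 0.40 = 8 points |

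**A bound that can be computed from a log.** Let N patients be approached and let s be the low-risk share, taken as equal in consenters and non-consenters. Those agreeing number w·s·c·N, and the low-risk patients approached number s·N. The ratio is c·w, because s cancels. So c·w is the lower bound on uptake if non-consenters have the same low-risk share and none would accept. It needs only the numbers approached and consenting.

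**Risk split.** Assume a true low-risk share of 60%. If low- and high-risk patients consent at 70% and 50%, the observed share is 0.42/(0.42 + 0.20) = 67.7%. If they consent at 50% and 70%, it is 0.30/(0.30 + 0.28) = 51.7%. With equal consent rates it is 60%. The split is conditional on consent, but the direction of any bias is unknown.

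**The case against.** The best reply is that much of the funnel is already planned. The total triaged and the reasons for failing to progress will be reported, and a refusal at consent is a failure to progress. WS-1 output item 7, on patients declining a DPC, is not restricted to the low-risk group. The triage proforma (Appendix 11.01) is not shown and may already hold the reason for refusal. Exact denominators are often left to an analysis plan. Low-risk patients are invited to the DPC as a separate step after stratification, and the protocol expects some to refuse there, so consent to the study is not the same as agreeing to a challenge. Some who refuse research might accept a DPC in routine care. Willingness is a secondary outcome; the primary acceptability outcome is a description of facilitators and barriers.

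Most of this stands, and it limits the size and weight of the point. It does not remove it. No listed measure of willingness uses the approached or triaged population, and item 7 states no denominator. The data-capture list in 10.4.3.3 names numbers triaged and stratified, but not numbers approached or refusing consent. The denominator follows from the protocol's recruitment order, and refusals not recorded at the time cannot be recovered by a later analysis plan. Acceptance by some research refusers shrinks the overstatement but leaves it positive while u < w.

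A reader might go further and infer that the cost-effectiveness result would be too favourable. The document does not support that. Section 10.4.5 names the risk split and DPC outcomes as inputs, not willingness. The risk split has no known direction of bias. The model is not yet built, and lower uptake would reduce both challenge costs and benefits.

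A reader might also want the low/high-risk split reported against everyone triaged. That figure could not be interpreted, because patients who do not consent have no risk status. Nor is the removal of serious non-immediate reactions at triage a distortion: the service model in 10.2.2 excludes them too.

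**Conclusion.** The point holds for the willingness outcome. As defined, it is willingness conditional on having joined the study, and it overstates willingness among labelled low-risk patients whenever non-consenters are less willing than consenters. The overstatement is (1-c)(w-u). Its size cannot be derived from the protocol: the four assumed cases above run from 8 to 54 points, and the larger values require that no non-consenter would accept a DPC. The upward direction rests on u < w, which is plausible but not documented. The low/high-risk split needs a label stating its condition, not a correction. Nothing here affects the 122 DPCs, and no conclusion about the direction of the WS3 result follows.

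**What to change.** Within the planned analysis of failed progression from triage:

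1. Count the patients approached and those refusing consent, and separate refusal to take penicillin from refusal to join research.
2. Report uptake twice: among consented low-risk patients, and as a lower bound among all triage-eligible patients approached. State the assumptions behind the bound: non-consenters have the same low-risk share and would not accept.
3. Label the low/high-risk split as conditional on consent.
4. If uptake is used in WS3, vary it over this range in the scenario analyses already planned in 10.4.5.

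The cost is small: a refusal reason on the triage log, if it is not already there, and an extra row in a table. Sample size, eligibility and procedures do not change. The downside is a less favourable uptake figure beside the planned one.
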